Participants: 70 overweight and obese healthy male and female volunteers aged between 18 and 65 years with body mass index (BMI) of 25-35 kg/m².

Support of number of volunteers: Based on previous work we anticipate that a hypo-caloric diet alone will cause a weight loss of 3.0 ± 2.5 kg, whilst the addition of propionate-ester will cause a weight loss of 5.0 ± 2.5 kg. A power calculation shows that 26 volunteers will be need per group to detect a significant difference between groups ($p=0.05$, 0.80 power). 70 volunteers will be recruited to allow a 25% drop-out rate.

Visit 1: Health Screening

Participants will attend the NIHR/Wellcome Trust Imperial Clinical Research Facility at Hammersmith Hospital where their eligibility will be assessed. They will have a blood test (FBC, ALT, HbA1C, renal function, and lipids) and height and weight measurements will also be taken. They will also have an electrocardiogram (ECG) and blood pressure will be recorded. All women of childbearing age will have a pregnancy test.

Participants will be told not to start any other new diets or intensive exercise regimes during the study period as this may give us conflicting results.

Visit 2: Acclimatization visit (Week 0)

The main objective of this visit is to fully acclimatize the participants to the study before the baseline visit.

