The same measurements collected during the acclimatization visit will be repeated. The only difference would be in collecting 10 ml of postprandial blood, instead of flushing saline, at each time point of 15, 30, 60, 90, 120, 180, and 240 min to measure hormones and metabolites. These will include glucose, insulin, gastrointestinal and appetite hormones (GLP-1, pro-glucagon-derived peptide, PYY, PP, Ghrelin, Cholecystokinin), and short chain fatty acids level

Participants will be randomised to take 10 g of Propionate ester or Inulin (control) dietary supplement once a day for 84 days (12 weeks). Supplements will be given to participants in ready-to-use sachets and instructed to mix the contents into their -500 kcal/day individual diet. An independent researcher (i.e. not linked to the study) will be given the task of randomisation, which will be by sealed envelopes.

Urine will be collected throughout the study visit to measure propionate and urea concentrations. Subjects will empty their bladder before the test breakfast and collect all urine thereafter for a period of 240 min. Subjects will be provided with an appropriate measurement container to collect urine and will be asked to note the total volume following each collection.

Subjects will be asked to collect a stool sample to assess propionate levels. Subjects will collect a sample of the first stool they pass after 10:00 pm on the study day. Participants will be provided with detailed instructions of how to do this and will be given appropriate containers.

Visits 4 and 5: Study visits 2, 3 (Week 4 and week 8):

Will involve short visits to monitor weight and dietary compliance to the diet, through collecting 7-days food intake diary and taking anthropometry measurements.

Visit 6: Study visit 4 (Week 12):

At the end of 84 day supplementation period, participants will attend the NIHR/Wellcome Trust Imperial Clinical Research Facility at Hammersmith Hospital to and all measurements collected during Study Visit 1 will be repeated.

PARTICIPANT ENTRY**INCLUSION CRITERIA**

- Healthy overweight and obese volunteers (body mass index (BMI) of 25-35 kg/m²)
- Age between 18-65 years (inclusive)
- Having blood results for the following tests in the ranges of:
 - HbA1C 20-41 mmol/mol haemoglobin
 - ALT 0-40 IU/L
 - FBC :

| TEST | MALE | FEMALE |
|---------------------------------|-------------|-------------|
| WBC (x10 ⁹ /L) | 4.2-10.6 | 4.2-11.2 |
| RBC (x10 ¹² /L) | 4.23- 5.46 | 3.73-4.96 |

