Statistical analysis perform with IBM SPSS version 23. Graphs prepare with GraphPad Prism version 7.04. Data will be checked for normality using a Shapiro-Wilk test (defined as $P \geq 0.01$). Percentage of weight loss will be calculated using the weight at the end of the intervention divided by the baseline weight multiplied by 100. The results express as mean difference with \pm SEM. Mean of data will be compared within and between groups using a paired t-test or Wilcoxon signed-rank test where applicable. Analysis of variance will assess the impact of two different interventions (IPE and Inulin) on participant blood parameters across the 12-week supplementation period (baseline and week 12), with the supplementation group used to determine between-subjects differences. A p-value ≤ 0.05 will consider significant.

References:

- Abete, I. et al., 2008. Effects of two energy-restricted diets differing in the carbohydrate/protein ratio on weight loss and oxidative changes of obese men. *International journal of food sciences and nutrition*, 60 Suppl 3(783016891), pp.1–13. Available at: <http://www.ncbi.nlm.nih.gov/pubmed/18654910>.
- Bouché, C. et al., 2002. Five-week, low-glycemic index diet decreases total fat mass and improves plasma lipid profile in moderately overweight nondiabetic men. *Diabetes Care*, 25(5), pp.822–828.
- Brown, A.J. et al., 2003. The orphan G protein-coupled receptors GPR41 and GPR43 are activated by propionate and other short chain carboxylic acids. *Journal of Biological Chemistry*, 278(13), pp.11312–11319.
- Chambers, E.S. et al., 2015. A novel dietary strategy to increase colonic propionate production in humans and improve appetite regulation and bodyweight management. *Nutrition Bulletin*, 40(3), pp.227–230. Available at: <http://doi.wiley.com/10.1111/nbu.12157>.
- Chambers, E.S. et al., 2014. Effects of targeted delivery of propionate to the human colon on appetite regulation, body weight maintenance and adiposity in overweight adults. *Gut*, 64(11), pp.1744–1754. Available at: <http://www.ncbi.nlm.nih.gov/pubmed/25500202>.
- Cleave, T.L., 1974. The Saccharine Disease - Chapter 5. In Bristol. Available at: http://journeytoforever.org/farm_library/Cleave/cleave_ch5.html [Accessed February 28, 2016].
- Cordain, L. et al., 2005. Origins and evolution of the Western diet : health implications for the. *The American Journal of Clinical Nutrition*, 81, pp.341–354.

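### No outcome is designated primary (weight loss is only implied), and about 18 outcomes share one unadjusted 0.05 threshold

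*Combined protocol and SAP*

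**What the plan says.** The Statistical Plan closes with its only decision rule: "A p-value ≤ 0.05 will consider significant". It does not restrict the rule to any outcome, and it gives no multiplicity adjustment or testing order. The words primary and secondary are not attached to any outcome anywhere in the document.

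The nearest thing to a main outcome is in section 2, under Support of number of volunteers. There "we anticipate that a hypo-caloric diet alone will cause a weight loss of 3.0 ± 2.5 kg", while "the addition of propionate-ester will cause a weight loss of 5.0 ± 2.5 kg", and the calculation concludes that "26 volunteers will be need per group to detect a significant difference between groups". The section 2 heading also names weight loss alone. Against that, the aim at the end of the Introduction gives appetite and weight loss together, unranked, and the document title lists appetite first.

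The Statistical Plan does not carry the powered measure forward. Its only defined weight outcome is relative: "Percentage of weight loss will be calculated" from the ratio of final to baseline weight.

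The visit descriptions add many further outcomes. Visit 3 alone lists glucose, insulin, "gastrointestinal and appetite hormones (GLP-1, pro-glucagon-derived peptide, PYY, PP, Ghrelin, Cholecystokinin), and short chain fatty acids level".

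**The concern.** A 5% threshold controls the error rate of one test. When any of many outcomes may support a claim of significance, and none is fixed beforehand as decisive, the trial-level chance of a false claim is higher than 5%. The plan as written would let a null weight result and one gut hormone at p = 0.04 be reported as a significant effect of the supplement.

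Even a reader who accepts weight loss as the intended main outcome cannot tell whether kg or percentage decides it. Both choices, which outcome and which weight measure, could be made after the results are known.

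**Working it through.** **1. The plan's own sample size.** Inputs from Support of number of volunteers: losses of 3.0 and 5.0 kg, SD 2.5 kg in each group, alpha 0.05, power 0.80, dropout 25%. The number of sides is not stated.

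- Standardised difference: (5.0 − 3.0)/2.5 = 0.8.
- Normal approximation, two-sided: n = 2(1.960 + 0.842)²/0.8² = 24.5, so 25 per group.
- Two-sample t test, two-sided: power 0.791 at 25 per group and 0.807 at 26, so 26 per group. A one-sided test would need about 20, so the stated 26 fits a two-sided test.
- Recruitment: 52/(1 − 0.25) = 69.3, so 70.

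The plan's figures are reproduced. They concern one between-group test of weight loss in kg.

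**2. Count of outcomes.**

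| Source | Outcomes | Number |
|---|---|---|
| Statistical Plan | percentage weight loss | 1 |
| Visit 2, repeated at Visit 3 | RMR, RQ | 2 |
| Visit 2, repeated at Visit 3 | appetite and satiety scales (counted once), breath hydrogen | 2 |
| Visit 2, repeated at Visit 3 | buffet intake | 1 |
| Visit 3 bloods | glucose, insulin, six gut peptides, SCFA (counted once) | 9 |
| Visit 3 urine | propionate, urea | 2 |
| Visit 3 stool | propionate | 1 |
| **Total** | | **18** |

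This leaves out food diaries and other anthropometry, and allows one between-group test per outcome.

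**3. Chance of at least one p ≤ 0.05 when no outcome truly differs.**

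Independent outcomes: 1 − 0.95^18 = 0.603.

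The documents give no correlations, so a common correlation ρ among the test statistics is assumed and varied. The chance is 1 minus the average of P(|Z| < 1.96 given a shared normal factor)^k over that factor. The row for 15 outcomes omits plasma SCFA, urine propionate and stool propionate, which the supplement is meant to change.

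| Outcomes | ρ = 0 | ρ = 0.3 | ρ = 0.5 | ρ = 0.8 |
|---|---|---|---|---|
| 18 | 0.603 | 0.509 | 0.398 | 0.216 |
| 15 | 0.537 | 0.457 | 0.361 | 0.202 |

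With 18 outcomes the figure passes below one half at ρ of about 0.32. If correlation is confined to one block of 8 outcomes and one of 3, with the other 7 independent, it is 0.576, 0.543 and 0.496 for within-block correlations of 0.3, 0.5 and 0.7.

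**4. Effect of the two possible remedies.**

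- One primary outcome, weight change in kg at two-sided 0.05: power 0.807 at 26 per group; 70 recruited, unchanged.
- All 18 kept confirmatory under Bonferroni: alpha 0.05/18 = 0.00278. Weight-loss power at 26 per group falls to about 0.41. Power of 0.80 would need 49 per group, or 98/0.75 = 131 recruited.

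**The case against.** The strongest reply is that weight loss is plainly the main outcome: it is the only one powered, the only one in the section 2 heading, and the only one with a derivation in the Statistical Plan. Much of this stands. A single between-group test of weight loss, fixed in advance, has a 5% error rate, and a hormone is not as likely a candidate for the decisive outcome as weight. But the implication does not settle kg against percentage, and it puts no limit on claims from the other outcomes.

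A reader might infer that a false significant result is more likely than not. The documents do not support that. It requires nearly independent outcomes and no true effect on any of them. The plan itself expects a 2 kg effect on weight and higher colonic propionate, so a significant result on those need not be false.

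A reader might also add a separate test at each of the seven post-breakfast sampling times. The Statistical Plan describes no such tests; its analysis of variance for blood parameters compares baseline with week 12. Within-group tests are planned, but weight loss is expected on diet alone, so a significant within-group change there need not be a false positive. Neither is counted in the figures above.

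**Conclusion.** The point holds in this form: no primary outcome is designated, the powered weight measure differs from the one defined for analysis, and about 18 outcomes share one unadjusted threshold. The chance of at least one false-positive between-group result is up to about 60%, and about 40% at a common correlation of 0.5. Removing the three propionate and SCFA exposure measures lowers these to about 54% and 36%. Even at a correlation of 0.8 it is about 22%, some four times the nominal 5%.

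These figures assume one between-group test per outcome, no true effect on any outcome counted, and correlations that the documents do not give. They describe the risk if any outcome may carry the conclusion; they do not describe a prespecified test of weight loss. The sample size calculation is sound and is not in question.

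**What to change.** Before the data are analysed, add to the Statistical Plan:

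*The primary outcome is the between-group difference (IPE v inulin) in change in body weight in kg from Visit 3 to Week 12, tested two-sided at 0.05. All other outcomes, including percentage weight loss, are secondary or exploratory. They are reported as between-group estimates with 95% confidence intervals, and no efficacy claim is based on an unadjusted p ≤ 0.05.*

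Kg is proposed because it is the measure already powered. If the sponsor prefers percentage, the power calculation should be restated in that unit. The Visit 3 description does not list body weight by name, so the text should confirm that baseline weight is taken there. If a confirmatory appetite claim is wanted, one named appetite outcome could be tested only after a significant weight result; this is optional.

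The cost is a few sentences. The sample size does not change. The downside is that fewer secondary results can be called significant.
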